2.2 Setting and Participants

2.2.1 Setting:

The study will be conducted in Cardiff and Vale University Health Board, with patients drawn from Cardiology clinics and inpatient wards. Follow-up assessments will be conducted at Cardiff School of Sport, a research facility at a university campus close to the main hospital.

2.2.2 Number of subjects planned:

10 patients. This will be sufficient to establish estimates of variability in the diastolic reserve index (see below), allow estimation of treatment difference and gauge acceptability.

2.2.3 Target population:

Subjects with HFpEF and chronotropic incompetence

2.3 Endpoints:

Systolic and diastolic longitudinal reserve index are calculated by the following formulae:

$$\begin{aligned}\text{Systolic reserve} &= \Delta s' \times [1 - (1/s'_{\text{rest}})] \\ \text{Diastolic reserve} &= \Delta e' \times [1 - (1/e'_{\text{rest}})]\end{aligned}$$

These are known to be impaired in patients with HFpEF and are a marker of adaptation to exercise in terms of filling pressures and left ventricular relaxation. Tan et al report a significant difference between the results seen with 56 patients with HFpEF and 27 control subjects on exercise echocardiography with semi-supine bicycle.¹⁶ Patient characteristics were similar to those of our proposed study group (EF >50%, NYHA II, HFpEF according to Vasan and Levy criteria).²⁸

We will therefore investigate diastolic and systolic reserve index as possible endpoints of a future study into the efficacy of CRT versus RRP in HFpEF patients.

2.4 Planned interventions:

Visit 1 – Baseline Assessments: Patients will undergo initial assessment of baseline characteristics by echocardiography, cardiopulmonary exercise testing, 6MWT and MLHFQ. (Visit length: approx. 4 hours)

Visit 2 - Device Implantation (≤ 7 days after baseline assessments completed): Eligible subjects will undergo implantation of a biventricular pacemaker under normal laboratory conditions. Patients will be randomised in a 1:1 ratio to receive either rate-responsive pacing (DDDR) or CRT. Patients will be blinded to their treatment allocation. They will return to pacing clinic a week later for a programming check; during this visit, they will also undergo a chest x-ray according to local protocol to ensure correct lead placement (Visit length: 1 day + 2 hours)

Visit 3 – Assessments and Device Reprogramming

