3.2 Study Extension: Targeted Multipoint Pacing

Once all subjects have completed 12 weeks of RRP and 12 weeks of CRT (in either order), provisional analysis of the data will be performed. If an incremental benefit is shown for CRT above the benefit of RRP, analysis of echocardiograms before and after CRT will be performed to elucidate the mechanisms. Subjects will be invited to participate in a study extension. The pacemakers will then be non-invasively programmed using multisite optimisation to administer optimised CRT targeted to the specific mechanism of action. Final assessments will occur after 12 weeks, following which the participant involvement will end.

If no incremental benefit is shown for CRT at the initial analysis, the study will end at this point (after 24 weeks).

Incremental benefit for CRT will be defined as a statistically significant difference between average values for RRP and for CRT in paired t-tests in one or more of the following parameters: a) echocardiographic: diastolic reserve index; systolic reserve index; left ventricular end-systolic volume; left ventricular end-diastolic volume; tricuspid regurgitant peak velocity; torsion and untwisting on strain imaging; global longitudinal strain; b) cardiopulmonary exercise testing: peak oxygen consumption; exercise duration; VE-VCO₂ slope; c) distance walked on 6-minute walk test.

Ongoing pacemaker function will be a clinical decision based on patient preference and objective markers such as 6MWT. Long-term pacemaker follow-up will take place at [name] CRT clinic at University Hospital of Wales. All medications can be continued as prescribed for the duration of the study, but medication changes should be noted during follow-up.

4. Criteria for Evaluation

At each 12-week stage, the following will be assessed:

1. Change in end-diastolic volume
2. Change in end-systolic volume
3. Change in ejection fraction (Simpson's Biplane method)
4. Change in left ventricular filling by pulsed-wave Doppler of mitral inflow (peak E and A wave velocities, E wave deceleration time, A wave duration, diastolic filling time (DFT))
5. Change in pulmonary venous Ar (Atrial reversal) duration.
6. Change in left and right ventricular isovolumic relaxation time (IVRT) and isovolumic contraction time (IVCT)
7. Change in peak diastolic suction velocity (V_p)
8. Change in peak systolic twist (torsion) and in untwisting rate on speckle tracking

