9. Myocardial velocity imaging (MVI) in basal anterior, inferior, septal and lateral walls to assess:
 - a. Change in peak systolic velocity (s')
 - b. Change in peak early diastolic wave velocity (e')
 - c. Change in time from onset of QRS to onset of s' wave
 - d. Change in time from onset of QRS to peak e' wave
10. Change in duration of pulmonary venous a wave
11. Change in peak longitudinal strain in 12 wall segments, and peak global longitudinal strain (GLS) in 12-segment model
12. Change in pulmonary pressures as measured by tricuspid regurgitant jet peak velocity
13. Change in above parameters on exercise echocardiography where feasible due to image quality
14. Change in peak oxygen consumption (VO_2 max) and slope of ventilation to carbon dioxide production (VE- VCO_2 slope) on exercise
15. Change in exercise capacity as defined by duration of exertion and work-level achieved on cardiopulmonary exercise testing
16. Change in blood pressure response to exercise
17. Change in distance walked on 6-minute walk test
18. Change in New York Heart Association Functional Class
19. Change in Minnesota Living with Heart Failure Questionnaire score

5. Statistical Analysis Plan

Enrolled subjects will be analysed in a per protocol fashion. Estimates of period effects will be made by performing an unpaired t-test on the mean difference between the two treatment orders. Carryover effects will be estimated by performing a t-test comparing the mean within patient score (the mean of the two period means for each patient) with the mean between the treatment arms. If significant period or carry-over effects exist, then only the first period will be analysed.

The change in exercise, echocardiographic, functional class and wellbeing parameters will be evaluated using paired sample t-tests. A Wilcoxon signed rank test will be employed as a test of robustness.

The settings in the study extension will be compared with the CRT programming during the initial crossover period for each patient using paired sample t-tests (this may have taken place in period 1 or period 2).

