Where normality of distribution is not found, attempts will be made to transform the data using a suitable mathematical function. Where this is not possible, the Mann-Whitney U test will be employed. Analysis of categorical data will be by Chi-squared tests. Normality will be evaluated using visual assessment histograms and Q-Q plots. Significance will be tested at the 95% confidence level for all analyses, including calculation of period and carry-over effects.

An intention to treat analysis will be reported if the drop-out rate exceeds 10%. Corrections for multiplicity will not be made due to the exploratory nature of this data. No subgroup analysis is planned. Where data is missing, analysis will only be completed if 80% or more of data is present. For each analysis performed, subjects with data missing will be excluded from the individual parameter analysis, but will be included where data is present. Interim analysis will not be performed, except in the event of study discontinuation. Study discontinuation will occur only in the event of safety concerns, as detailed below, or in the event of failure to recruit within the planned timeframe.

Drop-out rates and reasons will be recorded at each stage. This will be presented as a CONSORT diagram in the publication of study results.

All statistical analysis will be double-checked by a statistician prior to dissemination of study results.

6. Study Administration

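### The extension t-test reuses the CRT measurements that opened the extension and has no concurrent control, so it is biased against optimised CRT on the triggering parameters and cannot attribute any difference to the multisite settings

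*Combined protocol and SAP*

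**What the plan says.** Section 3.2 makes the extension conditional: it is offered "If an incremental benefit is shown for CRT above the benefit of RRP", and otherwise participation stops after 24 weeks. Benefit is defined there as a "statistically significant difference between average values for RRP and for CRT in paired t-tests in one or more of the following parameters". The list has 12 parameters (11 if torsion and untwisting count as one). Section 5 adds: "Corrections for multiplicity will not be made due to the exploratory nature of this data".

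Sections 2.4 and 3.2 then direct the multisite settings at whatever mechanism the crossover echocardiograms suggest. The extension lasts 12 weeks and ends with one set of assessments (Visit 6).

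For its analysis, Section 5 states: "The settings in the study extension will be compared with the CRT programming during the initial crossover period for each patient using paired sample t-tests". It notes that the CRT phase used as comparator "this may have taken place in period 1 or period 2". It also says: "Significance will be tested at the 95% confidence level for all analyses", with no exception for the extension.

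Under Section 2.4 the device returns to DDDR at Visit 4. Under Section 3.2 the provisional analysis waits until every patient has finished both periods. The documents describe no concurrent control, no repeat measurement under standard CRT, no adjustment for time and no blinding for the extension.

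**The concern.** Two separate problems affect the same test.

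**Selection.** A parameter triggers the extension when the observed mean CRT-RRP difference is large enough to be significant. With 10 patients, part of that difference is likely to be chance, and some of the chance sits in the CRT measurements. The extension value carries fresh error and the comparator does not, so the comparator flatters standard CRT on exactly those parameters. Because the settings are aimed at the mechanism found in the same data, these are also the parameters most likely to be read first.

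**Sequence.** The randomised crossover protects CRT against RRP. It does not protect extension against CRT, where optimisation is confounded with elapsed time, an intervening spell in DDDR mode and possible expectation.

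A p-value from this test could therefore be taken as evidence that multisite optimisation helps, harms or does nothing when the design cannot separate those explanations. The two problems can also pull in opposite directions.

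**Working it through.** **Plan's own figure.** The only figure is the sample size: "10 patients. This will be sufficient to establish estimates of variability in the diastolic reserve index". No effect size, SD or power is given for any comparison, so nothing can be reproduced. The results below are in SDs of a paired difference over assumed ranges.

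**Inputs.** n = 10 (Section 2.2.2). 5% level (Section 5; sidedness is not stated, two-sided assumed, so 2.5% each way). 12 trigger parameters (Section 3.2). Assumed: equal, independent normal errors at the RRP, CRT and extension visits; triggering in CRT's favour; all 10 patients continue.

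**1. How often chance alone opens the extension.** If CRT equals RRP on 12 independent parameters:
- any significant difference: 1 - 0.95^12 = 46.0% (11 parameters: 43.1%);
- in CRT's favour: 1 - 0.975^12 = 26.2% (11 parameters: 24.3%);
- in CRT's favour with error correlation 0.5 (simulated): about 17%.

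**2. Size a difference must reach.** The critical t on 9 df is 2.262, so the observed mean difference must exceed 2.262/√10 = 0.715 observed SDs. Smaller true effects are overstated whenever they trigger.

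**3. Bias on triggering parameters, optimised CRT truly equal to CRT.** With equal errors, half the overstatement lies in the CRT mean:

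bias = -(mean observed CRT-RRP difference given triggering - true difference)/2

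| True CRT-RRP effect | Mean observed when triggered | Bias (SD) | False 'worse' | False 'better' |
|---|---|---|---|---|
| 0 | 0.665 | -0.33 | 16% | 0.1% |
| 0.3 | 0.756 | -0.23 | 9% | 0.3% |
| 0.5 | 0.830 | -0.165 | 6% | 0.6% |
| 0.8 | 0.973 | -0.09 | 4% | 1.1% |
| 1.2 | 1.245 | -0.02 | 3% | 2.0% |

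The observed means and error rates are simulated. Example: -(0.756 - 0.3)/2 = -0.228.

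**4. Loss of power.** Without selection, a paired t-test with n = 10 detects a true added gain of 0.8 SD with power 61.6%. On triggering parameters this falls to 39%, 46% and 54% for true CRT-RRP effects of 0.3, 0.5 and 0.8 SD. Replacing the comparator in the simulation with a freshly measured CRT value returns the bias to 0.00 and power to 61-62%. The shared CRT error is therefore the cause.

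**5. Parameters that did not trigger.** Selection pushes these the other way: +0.01, +0.04 and +0.07 SD for true effects of 0, 0.3 and 0.5. The shift reaches +0.14 and +0.26 SD at 0.8 and 1.2, but by then only about 38% and 8% of parameters fail to trigger. Averaged over all 12 parameters in trials that open, the bias is about 0 to -0.03 SD with independent errors, and up to -0.13 SD with correlation 0.5 and no true effect.

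**6. Age of the comparator.** Visit 6 falls no earlier than week 24 + 12 = 36 (nominal weeks).
- CRT first: 36 - 12 = at least 24 weeks.
- CRT second: 36 - 24 = at least 12 weeks.

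The 40-week limit in Section 2.8 would cap these at 28 and 16 weeks. That leaves a wait of at most 40 - 36 = 4 weeks after Visit 4, which is hard to square with waiting for every patient to finish.

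**7. What drift would do.** With no added effect and before selection, an upward drift of 0.3 or 0.5 SD gives a false 'significantly better' in 13% or 29% of tests. A downward drift of 0.3 SD gives a false 'worse' in 34%, 26% and 19% of tests on triggering parameters, for true CRT-RRP effects of 0.3, 0.5 and 0.8 SD.

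**The case against.** The strongest reply is that the study is labelled exploratory, no objective in Section 2.1 covers the extension, and Section 5 openly says the CRT phase may be either period. That limits the importance of the point but does not answer it. Section 5 uses the exploratory label to waive multiplicity correction, not to drop significance testing.

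Section 2.5 argues that patients tend to stay stable and that e' responds beat to beat. This makes large drift less likely for some measures. The same section concedes that ventricular volumes change more slowly, and it is defending the crossover, not the extension.

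Several stronger readings are tempting but unsupported:

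- **Responders, or high CRT values, are selected.** The criterion acts on the trial-level CRT-RRP difference and subjects generally are invited. For volumes, tricuspid regurgitant velocity and VE-VCO2 slope, a favourable value would be low. The benefit definition itself states no direction.
- **Every extension test is materially biased by selection.** The bias against optimised CRT sits on triggering parameters and nearly vanishes when CRT has a large true effect.
- **Selection would manufacture a gain for optimised CRT.** On triggering parameters it hides one. A false gain there needs drift or expectation.
- **Patients are known to be unblinded.** The documents do not say what patients are told at Visit 5. Awareness is a reasonable inference from a conditional invitation, no more.
- **The plan treats the contrast as randomised.** It does not say so, and a paired t-test does not assert it.
- **The test can detect nothing.** It keeps some power; what it lacks is attribution.

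**Conclusion.** The concern holds in this limited form. On triggering parameters the comparison is biased against optimised CRT, by about a third of an SD if CRT truly does nothing beyond RRP and by almost nothing if its true effect is 1.2 SD. The false 'worse' rate falls from about 16% to 3% across that range. These sizes rest on assumed effects, equal independent visit errors, two-sided testing and full continuation; the documents supply none of the effect or variance inputs.

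The lack of attribution does not depend on those assumptions. For any parameter, a difference between the extension and a CRT value at least 12 or 24 weeks older, with time in DDDR mode before the extension starts and no concurrent control, cannot be credited to the multisite settings. The point is minor for the trial as a whole because the extension is optional and serves no listed objective.

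**What to change.** In Section 5:

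- Remove the significance test for the extension, and rule out any conclusion that optimised CRT is better or worse than standard CRT.
- Report the mean paired difference and its interval for each parameter, described as non-randomised, with no blinding described for this phase.
- Give the weeks elapsed between each patient's CRT assessment and extension assessment.
- Present triggering and non-triggering parameters separately. State that for triggering parameters both the estimate and its 95% CI are biased by selection and must not be read as a test. Changing from a p-value to an interval does not remove this: a 95% CI that excludes zero is the same test on the same comparator.

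The waiting time implied by Section 3.2 and the 40-week limit in Section 2.8 should also be reconciled.

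The cost is SAP wording only, with no change to visits, patients or procedures. The downside is that the extension yields no p-value and no efficacy claim.

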2.1 Objectives

The Primary Objective of this study is:

- To evaluate the feasibility and acceptability of using a randomised crossover trial design to assess efficacy of CRT versus rate-responsive pacing in patients with HFpEF

The Secondary Objectives of this study are:

- To evaluate the use of diastolic and systolic reserve index as end-points in a trial design comparing CRT with RRP in patients with HFpEF
- To establish appropriate secondary end-points for future studies into the effect of CRT on:
 - i. Longitudinal and global longitudinal strain, torsion and untwisting, and diastolic dyssynchrony at rest and on exercise echocardiography,
 - ii. Exercise duration and oxygen carrying capacity measured by cardiopulmonary exercise (CPEX) testing,
 - iii. Distance walked in a 6-minute walk test,
 - iv. New York Heart Association (NYHA) functional class,
 - v. Quality of life using the Minnesota Living with Heart Failure Questionnaire (MLHFQ)
- To establish the likely drop-out rate following recruitment for the trial in terms of failed implantation and patient disengagement
- To establish the number of participants required to appropriately power a further randomised trial of CRT versus RRP in patients with HFpEF
- To identify possible confounders and covariates to inform sample size calculations for future studies

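### The non-normal and categorical fallbacks (Mann-Whitney U, chi-squared) are unpaired tests and are not confined to unpaired comparisons, although the main comparisons of this crossover are within patient

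*Combined protocol and SAP*

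**What the plan says.** Every patient receives both pacing modes, and Section 5 (Statistical Analysis Plan) accordingly makes the main comparisons paired: "The change in exercise, echocardiographic, functional class and wellbeing parameters will be evaluated using paired sample t-tests". The extension settings are likewise to be "compared with the CRT programming during the initial crossover period for each patient using paired sample t-tests".

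Two rank tests then appear in different roles. The paired one is a sensitivity check: "A Wilcoxon signed rank test will be employed as a test of robustness". The unpaired one is the fallback for data that are non-normal and cannot be transformed, and chi-squared follows in the next sentence: "Where this is not possible, the Mann-Whitney U test will be employed. Analysis of categorical data will be by Chi-squared tests".

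Section 5 also contains comparisons that really are between patients: the period test, the carry-over test, and the rule "If significant period or carry-over effects exist, then only the first period will be analysed". The sentences naming Mann-Whitney and chi-squared do not refer to these or limit themselves to them. No paired categorical test is named anywhere.

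**The concern.** Mann-Whitney U and Pearson chi-squared assume that the two sets of readings come from different people. In RRP versus CRT and in extension versus CRT they come from the same people. An analyst who follows Section 5 literally on an endpoint that fails the normality check would leave the paired t-test for an unpaired rank test, and lose the pairing for which the crossover was chosen.

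Three consequences follow.

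- With positive within-patient correlation the Mann-Whitney test is miscalibrated: its true type I error lies below the nominal 5%.
- The same endpoint also has a planned signed rank result. The two can disagree, and the plan does not say which decides.
- NYHA class is ordinal. It is sent to a paired t-test as functional class and, if treated as categorical, to chi-squared as well. Neither suits paired ordinal data.

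This bears on a stated secondary objective, "To establish appropriate secondary end-points for future studies into the effect of CRT on" a list of measures. The documents do not say how endpoints will be chosen. If significance plays a part, a measure could be passed over because of the test used.

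**Working it through.** **Nothing to reproduce.** The plan gives no power, effect size, SD or within-patient correlation. Section 2.2.2 says only "10 patients. This will be sufficient to establish estimates of variability in the diastolic reserve index".

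**Inputs.** From the documents: 10 patients, each measured under both modes; 5% significance. Assumed: two-sided testing (sidedness is not stated) and within-patient correlation ρ of 0.3, 0.5, 0.7 or 0.9.

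**Illustration.** Take RRP readings 1, 2, …, 10 and CRT readings higher by 0.5, 0.6, 0.7, 0.8, 0.9, 1.1, 1.2, 1.3, 1.4, 1.5. All 10 patients improve. Exact signed rank: p = 2 × 0.5¹⁰ = 0.002. Exact Mann-Whitney: U = 41 out of 100, p = 0.53.

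**Size by formula (normal data, large sample).** Pairing shrinks the variance of the Mann-Whitney statistic by the factor f = 1 − (6/π)·arcsin(ρ/2), so the true size is about 2[1 − Φ(1.96/√f)]. At ρ = 0.5, f = 1 − 1.910 × 0.2527 = 0.517, 1.96/√0.517 = 2.72, and the size is 0.6%. At ρ = 0.3 it is 2.0%; at 0.7, 0.05%.

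**Size by simulation.** 20,000 trials per setting, 10 pairs, exact tests, normal data, no effect:

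| ρ | Mann-Whitney | Signed rank |
|---|---|---|
| 0.3 | 1.9% | 4.7–5.1% |
| 0.5 | 0.7% | 4.7–5.1% |
| 0.7 | 0.2% | 4.7–5.1% |
| 0.9 | 0.0% | 4.7–5.1% |

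Repeat runs agreed to within about 0.3 points, and non-normal shapes showed the same pattern. The sign of ρ matters: at ρ = −0.3 the Mann-Whitney size rises to 7.4%.

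**Power by simulation.** Effect equal to 1 SD of the within-patient difference; Mann-Whitney versus signed rank, in %:

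| ρ | Normal | Gamma (shape 1.5) | t, 3 df | Log-normal (log SD 0.8, shift) |
|---|---|---|---|---|
| 0.3 | 68 vs 78 | 81 vs 80 | 85 vs 85 | 91 vs 83 |
| 0.5 | 53 vs 79 | 70 vs 79 | 74 vs 85 | 86 vs 83 |
| 0.7 | 29 vs 79 | 51 vs 79 | 52 vs 85 | 73 vs 82 |
| 0.9 | 3 vs 78 | 11 vs 80 | 12 vs 85 | 29 vs 83 |

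The fallback applies only to non-normal data, so the last three columns matter most. They show no loss at 0.3. At 0.5 the result runs from a 3-point gain (86 − 83) to an 11-point loss (85 − 74). At 0.7 the loss is 9 to 33 points (82 − 73; 85 − 52), and at 0.9 it is 54 to 73 (83 − 29; 85 − 12).

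**Disagreement.** In those three shapes exactly one of the two rank tests is significant in 15–20% of trials at ρ = 0.5 and in 23–36% at 0.7. Some disagreement is unavoidable: at ρ = 0 it is already 10–14% (normal, log-normal and t).

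**Chi-squared.** For paired binary data (10 patients, probability 0.5, no continuity correction) the true size is 4.4, 1.6, 0.6 and 0.1% at ρ = 0, 0.3, 0.5 and 0.7. Exact McNemar at this sample size rejects even less often (about 1.0% at ρ = 0 and below 0.2% from 0.3). The point about chi-squared is therefore that it ignores the pairing; no power loss is claimed.

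**The case against.** The best defence is that Section 5 contains both paired and unpaired t-tests, and each rank test can be matched to its own t-test: signed rank for the paired changes, Mann-Whitney for period, carry-over and first-period analyses. On that reading nothing is wrong, and a valid paired rank result for RRP versus CRT will exist in any case. The reading is sensible, but the text does not state it. The signed rank test is expressly a check, and the fallback role goes to the other test without restriction.

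The size of the loss is also open to challenge, and much of this stands.

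- Fixing the effect at 1 SD of the difference shrinks the raw shift as correlation rises, to √(2 × 0.1) = 0.45 raw SD at 0.9. With a fixed shift of 0.8 raw SD, power at 0.9 is 79 vs 95% (log-normal), 55 vs 93% (gamma) and 63 vs 98% (t): losses of 16 to 38 points. A more skewed log-normal (log SD 1, correlation set on the log scale) gives 88 vs 92%. The same scaling shows losses of 5–8 points for gamma and t at 0.3, where the table shows none.
- A log transform would usually deal with the log-normal case, so it would seldom reach the fallback. How often any endpoint would do so is unknown, and the plan does not say whether normality is judged on raw values or on differences.
- NYHA class reaches chi-squared only if it is treated as categorical.

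Consequences are limited too. The primary objective is feasibility, the estimates of variability and treatment difference do not depend on the rank test, and the extension decision in Section 3.2 requires a "statistically significant difference between average values for RRP and for CRT in paired t-tests". Under positive correlation the error is on the conservative side. The planned check by a statistician may catch the problem, but it does not settle which test was prespecified.

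**Conclusion.** The concern holds. As worded, Section 5 assigns tests for independent groups to within-patient comparisons. The firm result is the calibration: with positive within-patient correlation, Mann-Whitney at nominal 5% has a true size of about 2% or less from a correlation of 0.3 upwards. The effect on power is real but depends on distribution, correlation and effect scaling: for the non-normal shapes studied it is absent or small at low correlation and substantial at 0.7 and above for most of them. The correlations are assumptions, and negative correlation would reverse the direction of the size error.

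The practical impact is modest. It reaches individual secondary comparisons that fail normality and transformation, and the handling of NYHA class. It does not reach the feasibility objective or the paired t-test rule for entering the extension. It should be fixed because the rule is wrong as written and the correct test is already in the plan.

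**What to change.** Reword the fallback sentences in Section 5:

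1. For within-patient comparisons (RRP versus CRT, extension versus CRT) that stay non-normal after transformation, the Wilcoxon signed rank test replaces the paired t-test as the deciding result. If adjustment for period is to be kept in RRP versus CRT, the alternative is Mann-Whitney on each patient's period 1 minus period 2 difference, compared between the two treatment orders. The SAP should name one of the two.
2. Mann-Whitney on raw values, and chi-squared, are limited to comparisons between the two orders, including a first-period-only analysis.
3. Take NYHA class out of the t-test list, analyse it by signed rank, and report the numbers improved, unchanged and worsened.

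The cost is about two sentences and no new data. Two limits should be acknowledged. With 10 patients any exact paired test of NYHA class has little power: at least 6 patients must change class to reach p < 0.05, since 5 all one way gives 2 × 0.5⁵ = 0.063 and 6 gives 2 × 0.5⁶ = 0.031. Signed rank is preferred to a sign or McNemar test because it uses the size of the change, but if every change is one class it reduces to the sign test. The period-adjusted alternative compares two small groups: with 5 patients per order its smallest two-sided p-value is 2/252 = 0.008, so significance remains attainable.

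### The 80%-of-data cut-off is undefined and can withhold the diastolic reserve index result, at three incomplete pairs of 10 on the natural reading, while adding almost no precision

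*Combined protocol and SAP*

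**What the plan says.** The rules are in section 5 (Statistical Analysis Plan) of the combined protocol and SAP.

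- **Cut-off:** "Where data is missing, analysis will only be completed if 80% or more of data is present". No unit, denominator or rationale is given.
- **Incomplete patients:** "subjects with data missing will be excluded from the individual parameter analysis, but will be included where data is present".
- **Test:** "The change in exercise, echocardiographic, functional class and wellbeing parameters will be evaluated using paired sample t-tests".
- **Analysis set:** "Enrolled subjects will be analysed in a per protocol fashion", and "An intention to treat analysis will be reported if the drop-out rate exceeds 10" per cent.
- **Record of losses:** "Drop-out rates and reasons will be recorded at each stage", shown in a CONSORT diagram.

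Three other places bear on these rules. Section 2.2.2 justifies 10 patients: "This will be sufficient to establish estimates of variability in the diastolic reserve index"; it adds estimation of the treatment difference and acceptability. Section 2.1 lists, as secondary objectives, evaluating the reserve indices as end-points and finding the number of participants for a further randomised trial. Section 4, item 13, expects incomplete exercise imaging: "Change in above parameters on exercise echocardiography where feasible due to image quality".

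**The concern.** The diastolic reserve index needs both resting and exercise e' (section 2.3), and a paired comparison needs it at both 12-week assessments. It is therefore among the endpoints most exposed to missing data, and it is the one whose variability is used to justify the sample size. A completeness rule that withholds its analysis works against that purpose.

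The rule is also undefined in two respects. The unit decides whether the same data set is analysed or barred, and as written that choice could be made after the data are seen. It is also open whether a barred analysis includes the descriptive mean difference and SD or only the test.

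At stake are the treatment-difference estimate, possibly the SD needed to size a further trial, and one route to the extension: under section 3.2, a parameter that is not tested cannot count towards incremental benefit. Low completeness would itself be useful feasibility information, but the plan requires only drop-out to be recorded, not the number evaluable per endpoint.

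**Working it through.** **Inputs.** From the documents: 10 patients, two period values each, 80% cut-off, 10% drop-out trigger, 95% confidence level (taken as two-sided). Assumed, because no rate is given: a chance p of 5%, 10% or 20% that the index is unobtainable at one visit. The choice of 10 patients cannot be reproduced, since no SD, effect size, power or target precision is stated.

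**Where the rule bites.**
- Complete pairs: 8/10 = 80% is analysed and 7/10 = 70% is not. The third incomplete pair bars the endpoint.
- Single values: three patients each missing one value leave 17/20 = 85%, which is analysed. Four missing values leave 16/20 = 80%, also analysed; five leave 15/20 = 75%, which is barred.

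**Chance of being barred, counting pairs.** P(X ≥ 3), X ~ Bin(10, q). If the same patients fail at both visits, q = p. If failures are independent between visits, q = 1 − (1 − p)².

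**Chance of being barred, counting single values.** With independent failures, P(Y ≥ 5), Y ~ Bin(20, p).

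| p per visit | Pairs, same patients fail twice | Pairs, independent | Single values, independent |
|---|---|---|---|
| 5% | 1.2% (q = 0.05) | 6.6% (q = 0.0975) | 0.3% |
| 10% | 7.0% (q = 0.10) | 29.2% (q = 0.19) | 4% |
| 20% | 32.2% (q = 0.20) | 76.0% (q = 0.36) | 37% |

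If the same patients fail at both visits, the two readings agree: two such patients leave 16/20 = 80% and three leave 14/20 = 70%, so the first column applies to both.

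If one of 10 randomised patients also drops out and pairs are counted, two further losses among nine suffice. P(X ≥ 2), X ~ Bin(9, q), is 7–22%, 23–53% and 56–89% at the three rates.

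**What the cut-off gains.** Half-width of the 95% CI for the mean paired difference, in SDs of the differences, is t(0.975, n−1)/√n. The 95% limits for the SD, as multiples of its estimate, are √[(n−1)/χ²].

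| Pairs | CI half-width | SD limits |
|---|---|---|
| 10 | 2.262/√10 = 0.715 | 0.69 to 1.83 |
| 8 (allowed) | 2.365/√8 = 0.836 | 0.66 to 2.04 |
| 7 (barred) | 2.447/√7 = 0.925 | 0.64 to 2.20 |

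The barred interval is 0.925/0.836 = 1.106 times as wide as one the rule accepts.

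**Drop-out trigger.** 1/10 = 10% does not exceed 10%; 2/10 = 20% does. If drop-outs leave no pair, three of them trigger the intention-to-treat report but leave 70% of pairs, which the 80% rule bars when pairs are counted.

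**The case against.** Several counter-arguments have force.

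- **The unit is open.** Counting single values with independent failures makes a barred endpoint much less likely. This stands, so both readings are shown. It also strengthens the case for a definition.
- **The rates are assumed.** The upper figures also need failures to be independent between visits, whereas poor image quality may recur in the same patient, which points to the lower figures. The appendix limits exercise to anaerobic threshold, allows three minutes of imaging per stage and provides a workload reduction so that scanning can finish. These steps should reduce losses. This stands; no single probability can be defended.
- **The SD may not be lost.** A reader might infer that the plan suppresses the SD and so defeats the sizing objective. The documents do not establish this: section 5 is written mainly about tests, and barring only the test is a fair reading. A further trial need not be a crossover either, and a parallel design would use a between-patient SD that needs no complete pairs.
- **A floor can guard against unrepresentative complete cases.** True, and going from 10 to 7 pairs widens the CI by 29% (0.925/0.715). But the rule does not restore lost pairs; it only withholds the result, and selection can be stated beside an estimate.
- **The intention-to-treat point is minor.** A reader might infer that as-randomised results are ruled out at or below 10% drop-out. The text makes them certain above 10% and is silent otherwise. A patient with no second period adds nothing to a paired t-test, so the two analyses would often agree. No per-protocol exclusion is stated, so a completer left out of that set is hypothetical.

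**Conclusion.** The concern holds in this form: the 80% rule is stated without unit, denominator or scope, and on its natural reading it bars an endpoint at 7 of 10 pairs, where precision is only about 11% worse than at the permitted 8. The diastolic reserve index can be that endpoint. How likely this is depends on unreadable rates that the documents do not give, and it ranges from negligible (0.3%) to more likely than not (76%) over the rates, readings and correlations considered.

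A stronger reading, that the pilot would fail in its purpose, is not supported. The primary objective of feasibility and acceptability is untouched by the cut-off, the study is exploratory, and the SD limits of 0.69 to 1.83 at a full 10 pairs show that imprecision comes mainly from the sample size. The drop-out trigger is a secondary matter. Its denominator is unclear because section 2.1 counts failed implantation as drop-out while section 3 randomises after successful placement. The point should be corrected, and the correction is cheap.

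**What to change.** In section 5:

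1. For every endpoint, whatever the completeness, report the available-data estimate with its 95% CI and SD, and the number evaluable at each visit as a feasibility result.
2. If a cut-off is kept, define it before data are seen as the share of randomised patients with both period values for that parameter, and let it bar only the significance test.
3. Report an as-randomised analysis beside the per-protocol one, without the 10% condition.
4. Count failed implants, which occur before randomisation, separately from drop-out after randomisation.

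The cost is a few sentences and one extra set of results. Some intervals will be wide, and estimates with many missing pairs may come from unrepresentative complete cases; the report should say so beside them.
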